9.1.1. Efficacy Parameters

9.1.1.1. Revised Hammersmith Scale

The RHS will be performed for the ambulatory patient subgroup (Cohort 1). Administration of the RHS includes the timed rise from floor and 10-Meter Walk/Run tests. The RHS is a 36-item clinical assessment for physical abilities of patients with Type 2 SMA, and ambulatory and nonambulatory patients with Type 3 SMA. The RHS includes 33 items that are graded on a scale of 0, 1, 2, where 0 denotes the lowest level of ability/function and 2 denotes the highest level of ability ([Ramsey 2017](#)). The remaining 3 items are scored 0, 1, where 0 denotes an inability and 1 denotes an ability to achieve. The maximum achievable score is 69.

9.1.1.2. 10-Meter Walk/Run

The 10-Meter Walk/Run test is an enhanced function of the RHS used for ambulant patients with Type 3 SMA. It is a measure of the time taken to walk/run 10 meters.

9.1.1.3. Timed Rise from Floor

The timed rise from floor test is an enhanced function of the RHS used for ambulant patients with Type 3 SMA. It is a measure of the time taken to rise to standing from the floor.

9.1.1.4. 6-Minute Walk Test

The 6MWT is an assessment of exercise capacity and fatigue that has been used in clinical studies of ambulatory patients with later-onset SMA ([Young 2016](#)). Ambulant patients in Cohort 1 will complete the 6MWT. Patients are directed to walk along a 25-meter course as fast as possible over 6 minutes. The minute distances and total distance walked over 6 minutes is measured.

9.1.1.5. 30-Second Sit-to-Stand

The 30-Second Sit-to-Stand Test is used by researchers and clinicians as an assessment of functional lower limb strength (Jones 1999). The test was modified for ambulatory SMA population based on recent research of the modified 30-Second Sit-to-Stand being a reliable, feasible tool for use in a general geriatric population with a lower level of function (McAllister 2019) and was related to fall risk in institutionalized veterans (Applebaum 2017, Le Berre 2016). The test measures the maximal number of times the patient can transition from sitting to standing in 30 seconds.

9.1.1.6. Hammersmith Functional Motor Scale Expanded

The HFMSE assesses the physical abilities of patients with Type 2 and Type 3 SMA (O'Hagen 2007; Glanzman 2011) and will be performed for nonambulatory patient subgroups (Cohorts 2 and 3). It consists of 33 items graded on a scale of 0, 1, 2, where 0 denotes unable, 1 denotes performed with modification or adaptation, and 2 denotes without modification or adaptation.

9.1.1.7. Revised Upper Limb Module

The RULM is a 20-item assessment of upper limb function in nonambulatory patients with SMA (young children as well as adults) (Mazzone 2017). The 19 scored items test functions that relate to everyday life, such as placing hands from lap, pressing a button, and picking up a token. The items are scored 0, 1, 2, where 0 denotes unable, 1 denotes able with modification, and 2 denotes able with no difficulty. The maximum score achievable is 37. Nonambulant patient subgroups (Cohorts 2 and 3) will perform the RULM. The RULM will be completed by patients who are 30 months of age or older at the time of the baseline assessment.

9.1.1.8. WHO Motor Development Milestones

The WHO Multicentre Growth Reference Study performance criteria is being utilized to assess motor development milestones of patients with Type 2 and nonambulatory Type 3 SMA enrolled in Cohort 2 and Cohort 3.

9.1.1.9. Endurance Shuttle Nine Hole Peg Test

The ESNHPT is an endurance test for severely affected patients with SMA. Patients are instructed to repeatedly perform the original 9 Hole Peg Test at 75% of their individual maximum speed. The shuttles refer to the set speed marked by auditory cues, with the test ending when the patient missed 2 consecutive beeps. The primary outcome parameter is “time to limitation (Tlim),” which is defined as the time a task can be maintained at the pre-set intensity. Maximum test duration is 20 minutes (Stam 2018). Nonambulant patients who score ≤ 3 on Item A of the RULM at Screening will perform the ESNHPT at Screening and all subsequent assessments. The ESNHPT will be completed by patients who are or will turn 8 years of age or older during the study. Patients who turn 8 years of age in Extension Periods A, B, or C who score ≤ 3 on Item A of the RULM at Screening should perform the ESNHPT as early as possible (preferred to begin at E1) and at all subsequent assessments until the end of the study.

9.1.1.10. Endurance Shuttle Box and Block Test

ESBBT is an endurance test for moderately affected patients with SMA. Patients are instructed to repeatedly perform the original Box and Block Test at 75% of their individual maximum speed. The shuttles refer to the set speed marked by auditory cues, with the test ending when the patient missed 2 consecutive beeps. The primary outcome parameter is Tlim. Maximal test duration is 20 minutes (Stam 2018). Nonambulant patients who score >3 on Item A of the RULM at Screening will perform the ESBBT at Screening and all subsequent assessments. The ESBBT will be completed by patients who are or will turn 8 years of age or older during the study. Patients who turn 8 years of age in Extension Periods A, B, or C who score >3 on Item A of the RULM at Screening should perform the ESBBT as early as possible (preferred to begin at E1) and at all subsequent assessments until the end of the study.

9.1.1.11. Pediatric Evaluation of Disability Inventory Computer Adaptive Test

A caregiver (who may or may not be a parent and/or legal guardian) must complete the PEDI-CAT Assessment. The PEDI-CAT Assessment should not be administered if a caregiver is not present. The PEDI-CAT Assessment should not be administered to the patient. The PEDI-CAT is a questionnaire completed by the caregiver that assesses the patient's ability to perform daily functions (Haley 2005). The PEDI-CAT is filled out by the caregiver in a location where they are not watching the patient perform any functional assessment tests. The same caregiver must fill out the assessment throughout the study duration. The answers are scored on a 4-point scale (unable to easy). The test is suitable to assess function in newborns to 21-year-olds; this questionnaire should be completed throughout the duration of the study (regardless of age). Properties of the PEDI-CAT have been studied in the SMA population. A Rasch analysis with results published in 2016 revealed that the distribution of abilities for the Mobility and Daily Activities domains of the PEDI-CAT are best represented in the Type 2 and Type 3 populations (Pasternak 2016). As the PEDI-CAT is an age-dependent questionnaire, a patient's full date of birth is required for accurate assessment.

9.1.1.12. Patient-reported Outcomes Measurement Information System

The Patient-reported Outcomes Measurement Information System (PROMIS) is a person-centered measure intended to be completed by the patient or parent proxy without help from anyone (Ader 2007). The fatigue profile domain measures a range of symptoms, from mild subjective feelings of tiredness to an overwhelming, debilitating, and sustained sense of exhaustion. The self-report measures are suitable for children 8-17 years old and the parent proxy report measures are suited for children 5-17 years old. If a caregiver completes this form, the same caregiver must complete the form throughout the study duration. Patients age 18 through 21 years old will complete an adult form of PROMIS. The PROMIS will be completed by patients who are or will turn 5 years of age or older at the time of the baseline assessment; the same questionnaire used at Screening should be used throughout the duration of the study (regardless of age).

9.2. Pharmacokinetics Blood Sample Collection

Blood samples for the measurement of SRK-015 concentrations will be obtained prior to study drug infusion as indicated in the schedule of assessments in Table 2, Table 3, Table 4, and

Table 5. In the Treatment Period, the 2-hour (± 1 hour) postdose (from the stop of the infusion) sample collection on Day 0, Day 140, and Day 336 must be collected via peripheral venipuncture. In Extension Periods A, B, and C, the 1-hour (+30-minute window) postdose (from the stop of the infusion) sample collection on Day 700, Day 1008, Day 1092, and Day 1428 must be collected via peripheral venipuncture.

Each collected sample will be split into approximately equal volume sample sets to allow for retesting, if required. Aliquots from the PK blood samples may be used for biomarker testing (Extension Period C only) or additional PD or immunogenicity testing as appropriate, and Baseline and postbaseline samples may be used to support PK, PD, and/or ADA assay validation.

9.3. Pharmacodynamics Blood Sample Collection

Blood samples will be collected for the measurement of latent myostatin levels. These blood samples will be obtained prior to infusion as indicated in the schedule of assessments in [Table 2](#), [Table 3](#), [Table 4](#), and [Table 5](#). The 2-hour (+30-minute window) postdose (from stop of infusion) sample collection on Day 0 must be collected via peripheral venipuncture. Each collected sample will be split into approximately equal volume sample sets to allow for retesting, if required. Aliquots from the PD blood samples may be used for biomarker testing (Extension Period C only) or additional PK or immunogenicity testing as appropriate, and Baseline and postbaseline samples may be used to support PK, PD, and/or ADA assay validation.

9.4. Immunogenicity Blood Sample Collection

Blood samples for the measurement of anti-SRK-015 antibodies will be obtained prior to infusion as indicated in the schedule of assessments in [Table 2](#), [Table 3](#), [Table 4](#), and [Table 5](#).

Each collected sample will be split into approximately equal volume sample sets to allow for retesting, if required. Aliquots from the immunogenicity samples may be used for biomarker testing (Extension Period C only) or additional PK or PD testing as appropriate, and Baseline and postbaseline samples may be used to support PK, PD, and/or ADA assay validation.

9.5. Biomarkers (Extension Period C Only)

Aliquots from PK, PD, and ADA serum samples collected during Extension Period C will be stored and may be used for exploratory biomarker testing. These samples may be used for research to develop methods, assays, prognostics, and/or companion diagnostics related to discovering and/or evaluating effects of SRK-015. Additional blood samples will not be collected for the purposes of biomarker testing.

10. ASSESSMENT OF SAFETY

10.1. Safety Parameters

10.1.1. Demographic/Medical History

Patient demographics and medical history will be recorded on the source document and electronic case report form (eCRF). Demographic characteristics include age, sex, race, and ethnicity. Medical history will capture the patient's SMA history as well as current and past relevant medical status (surgeries, allergies, and concomitant medications).

10.1.2. Vital Signs

Vital signs will be performed by the Investigator or his/her qualified designee according to the schedule of assessments provided in [Table 2](#), [Table 3](#), [Table 4](#), and [Table 5](#). Routine vital sign assessments will include heart rate, blood pressure, and respiratory rate to be collected in the Treatment Period at preinfusion, every 15 minutes (± 5 minutes) during the infusion from the start of the infusion, at the end of the infusion, and 1 and 2 hours (± 15 minutes) postinfusion. In Extension Periods A, B, and C, vital sign assessments will be collected at preinfusion, every 15 minutes (± 5 minutes) during the infusion (from the start of the infusion), at the end of the infusion, and 1 hour (± 15 minutes) postinfusion. Body temperature will be collected preinfusion.

10.1.3. Weight and Height

Weight and height will be collected according to the schedule of assessments provided in [Table 2](#), [Table 3](#), [Table 4](#), and [Table 5](#). Weight will be collected within 48 hours of each dose to calculate weight-based dosing and height will be collected at visits where the motor function outcome measures are conducted. Standing height will be collected for all individuals who are able to independently stand. Surrogate height may be estimated using ulna length if the patient is nonambulatory or needs standing support.

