2.3.2 Safety Endpoints

In this study, safety will be evaluated based on occurrence of:

- Treatment-emergent adverse events (TEAEs) and serious adverse events (SAEs); and
- Concomitant medications.

or changes from baseline in the following parameters:

- Vital signs, including blood pressure, heart rate, body temperature, and respiratory rate;
- Height and weight;
- Physical examinations;
- Laboratory assessments (hematology and coagulation, serum chemistry, urinalysis);
- 12-lead electrocardiogram (ECG); and
- Concomitant medications.

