2.3.2.5 Height, Weight and Body Mass Index (BMI)

Weight will be collected within 48 hours of each dose in order to calculate weight-based dosing, and height will be collected at visits where the motor function outcome measures are conducted.

Standing height will be collected for all individuals who are able to independently stand.

Surrogate height may be estimated using ulna length if the patient is nonambulatory or needs standing support.

The Gauld's equation (Gauld 2004) that is used for calculated height (in cm) using ulna length, for males:

$$\text{Estimated height} = (4.605 * \text{ulna length}) + (1.308 \times \text{age}^*) + 28.003$$

and for females:

$$\text{Estimated height} = (4.459 * \text{ulna length}) + (1.315 \times \text{age}^*) + 31.485$$

Where age^* is the patient's age if under 18, and 18 if patient is 18 or older.

The BMI will be derived as,

$$BMI = \frac{\text{Weight in kg}}{(\text{Height in cm} / 100)^2}$$

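### In patients under 18 measured by ulna, change from Baseline in height includes about 1.3 cm a year from the equation's age term alone, and the measuring method may change with standing ability

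*Combined protocol and SAP*

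**What the plan says.** SAP 2.3.2 (Safety Endpoints) states that safety will be evaluated on the occurrence of events "or changes from baseline in the following parameters", and the list that follows includes "Height and weight". The protocol synopsis also names height and weight among the parameters whose changes are evaluated.

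Protocol 10.1.3 sets two measuring rules. First: "Standing height will be collected for all individuals who are able to independently stand". Second: "Surrogate height may be estimated using ulna length if the patient is nonambulatory or needs standing support". SAP 2.3.2.5 repeats both. It then gives one equation per sex, the first introduced as the one "that is used for calculated height (in cm) using ulna length, for males". Each equation has an ulna term, an age term and a constant, and the age entered "is the patient's age if under 18, and 18 if patient is 18 or older". BMI is calculated from the resulting height.

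SAP 3.1.3 defines Baseline for all safety variables as the last measurement before the first dose, with no condition on how it was taken. Neither document holds one height method constant per patient, asks for both methods at a change-over, flags the method in the analysis, or plans to analyse ulna length itself.

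The trigger for ulna use is worded differently in different places. Protocol 10.1.3 and the Table 2 footnote refer to needing standing support, while the footnotes to Tables 3 to 5 refer to not being able to stand independently. A nonambulatory patient who can stand alone fits both measuring rules.

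**The concern.** An equation with an age term is an ordinary way to predict height at one visit. Differencing it within a patient is another matter: the age term contributes growth whether or not the bone has grown. Cohort 3 enrols from age 2, and Cohort 2 has no concurrent comparator, so growth there would be judged from within-patient change. A term that always rises pulls that change towards looking normal.

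The measuring rules also tie the method to motor status. A patient who gains independent standing moves from estimated to measured height, and one who loses it moves the other way. Attaining a new WHO milestone is a secondary endpoint in Cohorts 2 and 3, and standing alone is one of the six milestones. An outcome of the trial can therefore change how a safety parameter is measured.

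**Working it through.** The documents state no drift figure, so there is none to reproduce. The check evaluates the SAP 2.3.2.5 equations directly.

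**Inputs** (H and ulna length U in cm, age in years)
- Males: H = 4.605 × U + 1.308 × min(age, 18) + 28.003
- Females: H = 4.459 × U + 1.315 × min(age, 18) + 31.485
- Visit days, from the schedules of assessments: 364 (end of the Treatment Period), 728 (end of Extension Period A), 1092 (end of B), 1456 (end of C)

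**Step 1: drift with no ulna growth.** The constant cancels in a difference. With U unchanged and age under 18 throughout, the change is the age coefficient × day / 365.25.

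| Day | Males | Females |
|---|---|---|
| 364 | 1.308 × 364/365.25 = 1.30 cm | 1.315 × 364/365.25 = 1.31 cm |
| 728 | 2.61 cm | 2.62 cm |
| 1092 | 3.91 cm | 3.93 cm |
| 1456 | 5.21 cm | 5.24 cm |

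One year of the age term equals the contribution of 1.308/4.605 = 0.28 cm of ulna growth in males and 1.315/4.459 = 0.29 cm in females.

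**Step 2: limits set by age.** A patient starting at 17.5 years gains at most 0.5 × 1.308 = 0.65 cm (males) or 0.5 × 1.315 = 0.66 cm (females). A patient aged 18 or older gains nothing. The SAP does not say whether age is continuous or in completed years. In completed years, the 52-week drift is a step of 0 or about 1.3 cm, depending on whether a birthday falls in the interval.

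**Step 3: how many patients.** Cohorts 2 and 3 plan 15 + 20 = 35 of 55 patients. Cohort 1 patients must walk unaided at Screening, so they would be measured standing at Baseline. The 35 is a ceiling: ulna use is permitted rather than required, independent standers get standing height, and the age term is frozen from 18. The documents give no age distribution to narrow it.

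**Step 4: masking, on assumptions.** Suppose a male's usual growth is g cm per year, and slowed growth would lower true height growth in proportion to ulna growth. The share of a deficit that the estimate hides is then 1.308/g: 33%, 22% and 16% at assumed g = 4, 6 and 8. At g = 6, ulna growth is (6 − 1.308)/4.605 = 1.02 cm per year. If it halves, the estimate rises 4.605 × 0.51 + 1.308 = 3.65 cm, against a true 3.0 cm. Neither g nor the proportionality comes from the documents.

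**Step 5: BMI, on assumptions.** At constant weight, the relative change is (H0/H1)² − 1, where H0 and H1 are estimated height at Baseline and Day 364. For a male aged 5 with an assumed ulna of 15 cm, H goes from 103.6 to 104.9 cm and BMI falls 2.5%. For a male aged 13 with an assumed ulna of 22 cm, H goes from 146.3 to 147.6 cm and BMI falls 1.8%.

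**Step 6: method change.** The documents give no bias or agreement figure between standing and ulna-estimated height, and no expected number of patients crossing the standing threshold. Neither size nor frequency can be calculated.

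**The case against.** The strongest reply is that no height-change table is planned. SAP 3.6 covers vital signs, laboratory results, ECGs and adverse events, and protocol 11.2.1 does not name height. The only specified summary of height is as a baseline characteristic in SAP 3.3.4, where the equation is acceptable. This stands, and it limits the consequence. It does not remove the point: height is still a named change parameter, and SAP 2.3.2.5 is the only derivation a programmer would have.

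It is also fair that height is not an efficacy endpoint, dosing uses weight, no formal testing is planned, and physical examination and pubertal development are assessed separately.

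A reader might infer several stronger things that the documents do not support:
- That all 35 patients are affected. The 35 is a ceiling, as Step 3 shows.
- That the 5.2 cm figure belongs to the SAP's planned analysis. The SAP describes the study only through Extension Period B, extension analyses are exploratory under SAP 5.3, and Extension Period C appears only in the protocol. At the primary 12-month analysis the drift is about 1.3 cm.
- That 16% to 33% of any growth deficit is hidden. That range depends wholly on the assumptions in Step 4.
- That a method change puts a false jump into the patients whose motor function changes most. Only crossing the independent-standing threshold changes the method, and the size and direction of any shift are unknown.
- That the age term biases the Cohort 3 dose comparison. It adds essentially the same amount in both arms for patients under 18 measured by ulna.

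**Conclusion.** The point holds in a limited form. Followed as written, the plan gives a patient under 18 measured by ulna about 1.3 cm of estimated height gain by Day 364 with no ulna growth. The figure is about 3.9 cm through Extension Period B and 5.2 cm, in either sex, for patients who reach Day 1456. These figures follow from the SAP's own coefficients and assume continuous age, ulna used at both visits, and age under 18 throughout.

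The drift can partly mask slowed growth and lowers calculated BMI, but how much growth deficit it would hide cannot be stated without outside assumptions. It applies to an unknown number of patients, at most the 35 planned in Cohorts 2 and 3. The possible change of method is a gap in the rules, not a bias of demonstrated size. The primary efficacy results are unaffected. The correction is worth making because it is cheap and concerns a paediatric safety parameter.

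**What to change.** In SAP 2.3.2.5:
- Limit the equation to height and BMI at a single visit, and state which form of age is used.
- For change from Baseline, summarise change in measured ulna length for patients measured by ulna at both visits, and change in standing height for patients measured standing at both visits.
- Record a method flag at each visit and do not difference across methods.
- List patients whose method switches, with their within-method changes up to the switch.

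Patients who switch should not simply be dropped, because that would select on a post-baseline motor outcome. Their within-method visits before the switch stay in the summaries.

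The cost is SAP wording and one derived variable. The equation already requires ulna length, so no new assessment is needed. The downside is small: change in height is reported in two method-specific summaries, and visits after a switch are listed rather than summarised.

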10.1.4. Physical Examination

A complete physical examination will be performed by the Investigator or a qualified designee according to the schedule of assessments provided in [Table 2](#), [Table 3](#), [Table 4](#), and [Table 5](#). The findings of each examination will be recorded on the source documents and eCRF. The physical examination will include an assessment of the following: general appearance, skin, lymph nodes, head-eyes-ears-nose-throat, neck, abdomen, extremities, and the respiratory, cardiovascular, musculoskeletal, and neurologic body systems.

10.1.5. Electrocardiogram

A 12-lead electrocardiogram (ECG) will be collected at the times indicated in [Table 2](#), [Table 3](#), [Table 4](#), and [Table 5](#). ECGs are to be performed with the patient having rested for at least 5 minutes before each reading. ECGs are to be performed in triplicate, each at least 1 to 2 minutes apart. On infusion days, ECG will be collected within 2 hours prior to the start of the infusion and within 1 hour after the end of infusion at Visits EC1 and EC13. ECGs will be sent to a central reading vendor for assessment.

